1. INTRODUCTION

The purpose of this SAP is to describe the planned statistical analyses for Study RSV OA=ADJ-018 (219238).

1.1. Objectives, Estimands and Endpoints

Objectives	Endpoints and estimands
Primary*	

 To demonstrate the NI of the humoral immune response in healthy participants 50-59 YOA compared to OA (≥ 60 YOA) for the RSV-A strain after RSVPreF3 OA investigational vaccine administration. 	
 RSV-A neutralization titers expressed as group GMT ratio (OA-RSV/Adults-HA-RSV), 1 month after the RSVPreF3 OA investigational vaccine administration. RSV-A neutralization titers expressed as group SRR difference (OA-RSV - Adults-HA-RSV), 1 month after the RSVPreF3 OA investigational vaccine administration compared to baseline.

 To demonstrate the NI of the humoral immune response in healthy participants 50-59 YOA compared to OA (≥ 60 YOA) for the RSV-B strain after RSVPreF3 OA investigational vaccine administration. 	
 RSV-B neutralization titers expressed as group GMT ratio (OA-RSV/Adults-HA-RSV), 1 month after the RSVPreF3 OA investigational vaccine administration. RSV-B neutralization titers expressed as group SRR difference (OA-RSV - Adults-HA-RSV), 1 month after the RSVPreF3 OA investigational vaccine administration compared to baseline.

 To demonstrate the NI of the humoral immune response in participants 50-59 YOA at increased risk of RSV-LRTD compared to OA (≥ 60 YOA) for the RSV-A strain after RSVPreF3 OA investigational vaccine administration. 	
 RSV-A neutralization titers expressed as group GMT ratio (OA-RSV/Adults-AIR-RSV), 1 month after the RSVPreF3 OA investigational vaccine administration. RSV-A neutralization titers expressed as group SRR difference (OA-RSV - Adults-AIR-RSV), 1 month after the RSVPreF3 OA investigational vaccine administration compared to baseline.

 To demonstrate the NI of the humoral immune response in participants 50-59 YOA at increased risk of RSV-LRTD compared to OA (≥ 60 YOA) for the RSV-B strain after RSVPreF3 OA investigational vaccine administration. 	
 RSV-B neutralization titers expressed as group GMT ratio (OA-RSV/Adults-AIR-RSV), 1 month after the RSVPreF3 OA investigational vaccine administration. RSV-B neutralization titers expressed as group SRR difference (OA-RSV - Adults-AIR-RSV), 1 month after the RSVPreF3 OA investigational vaccine administration compared to baseline.
Secondary - Safety	

 To evaluate the safety and reactogenicity after the RSVPreF3 OA investigational vaccine administration. 	
 Percentage of participants reporting each solicited administration site event with onset within 4 days after study intervention administration (i.e., the day of study intervention administration and 3 subsequent days). Percentage of participants reporting each solicited systemic event with onset within 4 days after study intervention administration (i.e., the day of study intervention administration and 3 subsequent days).

[figure not shown]
Objectives	Endpoints and estimands
	
 Percentage of participants reporting unsolicited AEs within 30 days after study intervention administration (i.e., the day of study intervention administration and 29 subsequent days). Percentage of participants reporting any SAEs and pIMDs after study intervention administration (Day 1) up to Month 6. Percentage of participants reporting SAEs and pIMDs related to study intervention administration after study intervention administration (Day 1) up to study end (Month 12). Percentage of participants reporting any fatal SAEs after study intervention administration (Day 1) up to study end (Month 12).
Secondary - Immunogenicity	

 To evaluate the humoral immune response to the RSVPreF3 OA investigational vaccine until 12 months post-study intervention administration. 	
 RSV-A and RSV-B neutralization titers expressed as GMT, at pre-study intervention administration, 1 month, 6 months and at 12 months after study intervention administration.

 To evaluate the CMI response after RSVPreF3 OA investigational vaccine administration until 12 months post-study intervention administration. 	
 CMI response expressed as group geometric mean of the frequency of RSVPreF3-specific CD4+ and/or CD8+ T cells expressing at least 2 activation markers including at least 1 cytokine among CD40L, 4-1BB, IL-2, TNF-α, IFN-γ, IL-13, IL-17, at pre-study intervention administration, 1 month, 6 months and at 12 months after study intervention administration, in a subset of participants.
Tertiary	

(Note that tertiary objectives, endpoints, and estimands are optional and might be assessed only if needed; therefore, not all testing might be performed and reported)
	

CC1
	

AE=Adverse event; AIR=At increased risk; CD=Cluster of differentiation; CD40L=CD40 ligand; CMI=Cell-mediated immunity; GMT=Geometric mean titer; HA=Healthy adults; IFN=Interferon; IL=Interleukin; LRTD=Lower respiratory tract disease; NI=Non-inferiority; OA=Older adults; pIMD=Potential immune-mediated disease; RSV=Respiratory syncytial virus; SAE=Serious adverse event; SRR=Seroresponse rate; TNF=Tumor necrosis factor; YOA=Years of Age.

Primary estimands

The primary scientific question of the study is to demonstrate the non-inferiority of the immune response of RSVPreF3 OA investigational vaccine in healthy adults 50-59 years of age (YOA) and adults 50-59 years at increased risk of RSV-lower respiratory tract disease (LRTD), versus adults ≥ 60 YOA, in terms of RSV-A and RSV-B neutralizing titer (ED60) group GMT ratios and SRR difference at 1 month after vaccination in eligible participants who complied with the study requirements as defined per protocol (refer to Section 3 for the definition of the PPS used for the primary analysis and to Section 4.2 for the statistical methods).

1.2. Study Design

Overview of Study Design and Key Features	
Design Features	Phase 3 study to demonstrate the non-inferiority of the immune response of RSVPreF3 OA investigational vaccine in adults 50-59 years of age (YOA), including those who are at increased risk of RSV-lower respiratory tract disease (LRTD), versus adults ≥ 60 YOA. Blinding: observer-blind for Cohort 1, and open-label for Cohort 2. The study will be conducted in an observer-blind manner for Cohort 1 from study start-up to Day 31 analysis, beyond which the study will be considered single-blind (see Section 4.7.1 for details).
Study intervention	Participants will receive a single dose of study intervention (either RSVPreF3 OA investigational vaccine or placebo) at Visit 1 (Day 1).
Study cohorts, groups	Cohort 1 (adults 50-59 YOA), with 2 sub-cohorts (Adults-HA and Adults-AIR) and 4 parallel groups: 
 Adults-HA-RSV Group Adults-HA-Placebo Group Adults-AIR-RSV Group Adults-AIR-Placebo Group Cohort 2 (adults ≥ 60 YOA) with a single group (OA-RSV Group)
Study intervention Assignment	
 Participants in Cohort 1, Adults-HA Sub-cohort will be randomly assigned to the Adults-HA-RSV Group and Adults-HA-Placebo Group in a 2:1 ratio at Visit 1 (Day 1) to receive the RSVPreF3 OA investigational vaccine or placebo, respectively. Participants in Cohort 1, Adults-AIR Sub-cohort will be randomly assigned to the Adults-AIR-RSV Group and Adults-AIR-Placebo Group in a 2:1 ratio at Visit 1 (Day 1) to receive the RSVPreF3 OA investigational vaccine or placebo, respectively. All participants in Cohort 2 (OA-RSV Group) will be assigned to receive the RSVPreF3 OA investigational vaccine. The randomization algorithm will use a stratification by healthy/at increased risk status and CMI subset (participant included in the CMI subset or not) and a minimization procedure accounting for the study and center within each stratum. Minimization factors will have equal weight in the minimization algorithm.
Primary Completion Achieved (PCA) Analysis	A first analysis will be performed on all immunogenicity, reactogenicity and safety data available and as clean as possible, when data for at least primary and secondary endpoints up to Visit 2 (Day 31) are available for all participants.
Month 6 Analysis	A second analysis will be performed on all immunogenicity and safety data available and as clean as possible, when data for at least secondary endpoints up to Visit 3 (Month 6) are available for all participants.
End-of-study Analysis	An end of study analysis will be performed when all data for at least secondary endpoints up to study conclusion (Visit 4, Month 12) will be available for all participants.

2. STATISTICAL HYPOTHESES

[figure not shown]
Statistical hypotheses are associated to the confirmatory primary NI objectives, which will be tested according to the graphical procedure detailed in Section 2.1. Global type I error is controlled at 2.5% (1-sided).

Table 1 Study objectives and null hypothesis

Objectives	Null hypothesis
Primary	
a. To demonstrate the NI of the humoral immune response in healthy participants 50-59 YOA compared to OA (≥ 60 YOA) for the RSV-A strain after RSVPreF3 OA investigational vaccine administration.	
 Null hypothesis 1 (H1): The anti-RSV-A GMT ratio (OA-RSV Group over Adults-HA-RSV Group) is >1.5 or the SRR difference (OA-RSV Group – Adults-HA-RSV Group) is $>10\%$ at 1 month post RSVPreF3 OA vaccine administration. This must be rejected in favor of the alternative hypothesis that the GMT ratio is ≤ 1.5 and the SRR difference is $\leq 10\%$.
b. To demonstrate the NI of the humoral immune response in healthy participants 50-59 YOA compared to OA (≥ 60 YOA) for the RSV-B strain after RSVPreF3 OA investigational vaccine administration.	
 Null hypothesis 2 (H2): The anti-RSV-B GMT ratio (OA-RSV Group over Adults-HA-RSV Group) is >1.5 or the SRR difference (OA-RSV Group – Adults-HA-RSV Group) is $>10\%$ at 1 month post RSVPreF3 OA vaccine administration. This must be rejected in favor of the alternative hypothesis that the GMT ratio is ≤ 1.5 and the SRR difference is $\leq 10\%$.
c. To demonstrate the NI of the humoral immune response in participants 50-59 YOA at increased risk of RSV-LRTD compared to OA (≥ 60 YOA) for the RSV-A strain after RSVPreF3 OA investigational vaccine administration.	
 Null hypothesis 3 (H3): The anti-RSV-A GMT ratio (OA-RSV Group over Adults-AIR-RSV Group) is >1.5 or the SRR difference (OA-RSV Group – Adults-AIR-RSV Group) is $>10\%$ at 1 month post RSVPreF3 OA vaccine administration. This must be rejected in favor of the alternative hypothesis that the GMT ratio is ≤ 1.5 and the SRR difference is $\leq 10\%$.
d. To demonstrate the NI of the humoral immune response in participants 50-59 YOA at increased risk of RSV-LRTD compared to OA (≥ 60 YOA) for the RSV-B strain after RSVPreF3 OA investigational vaccine administration.	
 Null hypothesis 4 (H4): The anti-RSV-B GMT ratio (OA-RSV Group over Adults-AIR-RSV Group) is >1.5 or the SRR difference (OA-RSV Group – Adults-AIR-RSV Group) is $>10\%$ at 1 month post RSVPreF3 OA vaccine administration. This must be rejected in favor of the alternative hypothesis that the GMT ratio is ≤ 1.5 and the SRR difference is $\leq 10\%$.

2.1. Multiplicity Adjustment

The following graphical testing procedure will be applied to control the global type I error at 2.5% (1-sided) [Bretz, 2009].

Refer to Table 1 where H1/H2/H3/H4 labels are assigned.

The initial allocation of α among the null hypotheses is $(0.025, 0, 0, 0)$, while the propagation rules are specified by the transition matrix:

$$\begin{pmatrix} 0 & 0.5 & 0.5 & 0 \\ 0 & 0 & 1 & 0 \\ 0 & 0 & 0 & 1 \\ 0 & 1 & 0 & 0 \end{pmatrix}$$

3. ANALYSIS SETS

Analysis Set	Definition / Criteria	Analyses Evaluated
Screened Set	All participants who were screened for eligibility.	Study Population
Enrolled Set	All participants who entered the study (who were randomized or received study intervention or underwent a post-screening study procedure). NOTE: screening failures (who never passed screening even if rescreened) and participants screened but never enrolled into the study (met eligibility but not needed to reach the target enrolment) are excluded from the Enrolled Set as they did not enter the study.	Study Population
Exposed Set	All participants who received the study intervention. Analysis per group is based on the administered intervention.	Study Population, Safety
Per-Protocol Set*	All eligible participants who received the study intervention as per protocol, had immunogenicity results pre- and post-dose, complied with blood draw intervals, without intercurrent conditions that may interfere with immunogenicity and without prohibited concomitant medication/vaccination. Analysis per group is based on the administered intervention.	Immunogenicity

* Contribution of participants to PPS will be defined by timepoint.

3.1. Criteria for eliminating data from Analysis Sets

Elimination codes will be used to identify participants to be eliminated from analysis. Details are provided below for the Enrolled Set, the Exposed Set (ES) and the Per Protocol Set (PPS).

3.1.1. Elimination from Enrolled Set

The following codes will be used for identifying participants to be eliminated from the Enrolled Set:

- Code 800 (Fraudulent data)
- Code 900 (Invalid informed consent)

3.1.2. Elimination from ES

The following codes will be used for identifying participants to be eliminated from the ES:

- Code 800 (Fraudulent data)
- Code 900 (Invalid informed consent)
- Code 1030 (Study intervention not administered at all)
- Code 1100 (OA-RSV Group administered with placebo)

3.1.3. Elimination from PPS

A participant will be excluded from the populations for analysis under the following conditions:

- For codes 800, 900, 1030, 1050, 1070, 1080, 1090, 1100 and 2010: participants will be eliminated for all visits.
- For codes 1040, 1060, 2040 and 2050: participants will be eliminated from a specific visit (at which the condition is met) onwards.
- For codes 2020, 2090, 2100, 2120: participants will be eliminated at the specific visit at which the condition is met.

Table 2 List of elimination codes

Code	Condition under which the code is used	Visit / Contact (timepoints) where the code is checked	Applicable for analysis set/endpoint
800	Fraudulent data	All	Enrolled Set, ES, PPS
900	Invalid informed consent	All	Enrolled Set, ES, PPS
1030	Study intervention not administered at all	All	ES, PPS
1040	Administration of concomitant vaccine(s) forbidden in the protocol: 
 • Use of any investigational or non-registered vaccine other than the study intervention during the period beginning 30 days before the dose of study intervention, or planned use during the study period. • Planned or actual administration of a vaccine not foreseen by the study protocol in the period starting 30 days before and ending 30 days after the dose of study intervention administration, with the exception of inactivated and subunit influenza vaccines or COVID-19 vaccines (fully licensed or with EUA) which can be administered up to 14 days before or from 14 days after the study intervention administration. * • Previous vaccination with an RSV vaccine, including investigational RSV vaccines. 	All	PPS

Code	Condition under which the code is used	Visit / Contact (timepoints) where the code is checked	Applicable for analysis set/endpoint
1050	Randomization failure: participant not randomized in the correct stratum	Visit 1	PPS
1060	Randomization code was broken	All	PPS
1070	Vaccine administration not according to protocol: 
 • Participant was vaccinated with the correct vaccine but containing a lower volume • Wrong replacement or study vaccine administered (not compatible with the vaccine regimen associated to the treatment number) • Route of the study vaccine is not intramuscular • Wrong reconstitution of administered vaccine 	Visit 1	PPS
1080	Vaccine administration after a temperature deviation Vaccine administered despite a Good Manufacturing Practices (GMP) no-go temperature deviation	Visit 1	PPS
1090	Vaccine administration after expiration	Visit 1	PPS
1100	Other deviations related to wrong study treatment/administration/dose: OA-RSV Group = Administration of placebo	Visit 1	ES, PPS
2010	Protocol deviation linked to inclusion/exclusion criteria	All	PPS
2020	All Pre-dose results are missing	Visit 1	PPS
2040	Administration of any medication forbidden by the protocol 
 • Use of any investigational or non-registered product (drug or medical device) other than the study intervention during the period beginning 30 days before the dose of study intervention, or planned use during the study period. • Chronic administration of immune-modifying drugs (defined as more than 14 consecutive days in total) and/or administration of long-acting immune modifying treatments or planned administration at any time up to the end of the study. 
 – Up to 3 months prior to the study intervention administration: 
 ○ For corticosteroids, this will mean prednisone ≥ 20 mg/day, or equivalent. Inhaled and topical steroids are allowed. ○ Administration of immunoglobulins and/or any blood products or plasma derivatives. • Up to 6 months prior to study intervention administration: long-acting immune modifying drugs including among others immunotherapy (e.g., TNF-inhibitors), monoclonal antibodies, antitumoral medication. 	All	PPS
2050	Intercurrent medical condition: Participants may be eliminated from the PPS for immunogenicity if, during the study, they incur a condition that has the capability of altering their immune response or are confirmed to have an alteration of their initial immune status.	All	PPS
2090	Participants did not comply with blood sample schedule*:	Visit 2, Visit 3, Visit 4	PPS

Code	Condition under which the code is used	Visit / Contact (timepoints) where the code is checked	Applicable for analysis set/endpoint
	
 Number of days between vaccination (Visit 1) and blood sample (Visit 2) is outside [30-42] days. Number of days between vaccination (Visit 1) and blood sample (Visit 3) is outside [180-210] days. Number of days between vaccination (Visit 1) and blood sample (Visit 4) is outside [350-380] days. 		
2100	Immunological results not available post-vaccination	Visit 2, Visit 3, Visit 4	PPS
2120	Obvious incoherence/abnormality or error in laboratory data 
 Unreliable released data as a result of confirmed sample mismatch or confirmed inappropriate sample handling at laboratory. 	All	PPS

* Note: In case an emergency mass vaccination for an unforeseen public health threat (e.g.: a pandemic) is recommended and/or organized by the public health authorities, outside the routine immunization program, the time period described above can be reduced if necessary for that vaccine provided it is used according to the local governmental recommendations and that the Sponsor is notified accordingly.

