
 
To demonstrate the NI** of the humoral immune response in participants 50-59 YOA at increased risk of RSV-LRTD compared to OA (≥60 YOA) for the RSV-B strain after RSVPreF3 OA investigational vaccine administration.
 
	
 
RSV-B neutralization titers expressed as group GMT ratio (OA-RSV/Adults-AIR-RSV), 1 month after the RSVPreF3 OA investigational vaccine administration***.
 
RSV-B neutralization-titers expressed as group SRR difference (OA-RSV - Adults-AIR-RSV), 1 month after the RSVPreF3 OA investigational vaccine administration compared to baseline***.
 
			
Secondar	y - Safety			
To evaluate the safety and reactogenicity after the RSVPreF3 OA investigational vaccine administration.	
 
Percentage of participants reporting each solicited administration site event with onset within 4 days after study intervention administration (i.e., the day of study intervention administration and 3 subsequent days).
 
Percentage of participants reporting each solicited systemic event with onset within 4 days after study intervention administration (i.e., the day of study intervention administration and 3 subsequent days).
 
Percentage of participants reporting unsolicited AEs within 30 days after study intervention administration (i.e., the day of study intervention administration and 29 subsequent days).
 
Percentage of participants reporting any SAEs and pIMDs after study intervention administration (Day 1) up to Month 6.
 
Percentage of participants reporting SAEs and pIMDs related to study intervention administration after study intervention administration (Day 1) up to study end (Month 12).
 
Percentage of participants reporting any fatal SAEs after study intervention administration (Day 1) up to study end (Month 12).
 
			
Secondary - In	nmunogenicity			
To evaluate the humoral immune response to the RSVPreF3 OA investigational vaccine until 12 months post-study intervention administration.	RSV-A and RSV-B neutralization-titers expressed as GMT, at pre-study intervention administration, 1 month, 6 months and at 12 months after study intervention administration.			

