### 4.2.1. Rationale for the use of placebo

As there is currently no licensed RSV vaccine available, placebo groups (receiving saline solution) will be used as control for the safety/reactogenicity assessments.

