### 5.2. Exclusion criteria

The following criteria should be checked at the time of study entry. The potential participant MUST NOT be included in the study if ANY exclusion criterion applies:

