# 6.8. Concomitant therapy (Amended: 25 May 2023)

At each study visit/contact, the investigator(s) or their delegate(s) should question the participant about all medications/products taken, and vaccinations received by the participant.

The following concomitant medication(s)/product(s)/vaccine(s) must be recorded in the eCRF:

- All concomitant medication including vaccines/products, except vitamins and dietary supplements, administered during the 30-day period after the dose of study intervention (Day 1 to Day 30).
- All concomitant medication leading to elimination from the analysis, including products/vaccines. Please refer to the Section 5.2.2 for further details.
- All concomitant medication which may explain/cause/be used to treat an SAE/pIMD including vaccines/products, as defined in Section 8.3.1 and Section 10.3.8. These must also be recorded in the Expedited Adverse Event Report.
- For all AF AESIs (including serious and non-serious), concomitant drugs which could be associated with development or worsening of AF must be reported in the AF follow-up questionnaire.
- Any prophylactic medication (e.g., analgesics, antipyretics) administered on the day of study intervention administration (Day 1) in the absence of ANY symptom and in anticipation of a reaction to the study intervention administration.

Refer to Table 7 for an overview of the timing for recording of concomitant medication during the study.

The LML should be contacted if there are any questions regarding concomitant or prior therapy.

Table 7 Timing of collection of concomitant medication to be recorded (Amended: 25 May 2023)

	Dose 1 Day 1	Day 30	Study conclusion (Visit 4 at Month 12)
All concomitant medication including vaccines/products, except vitamins and dietary supplements		•	·
All concomitant medication including products/vaccines leading to elimination from the analysis			
All concomitant medication including vaccines/products which may explain/cause/be used to treat an SAE/ pIMD/ AF* )			
Any prophylactic medication			

**AF: Atrial Fibrillation;** p**IMD**=Potential immune-mediated disease; SAE=Serious adverse event. Note: The collection period for the concomitant medications to be recorded in eCRF is indicated in gray. **AESI= Adverse event of specific interest** 

\* For all AF AESIs (including serious and non-serious), concomitant drugs which could be associated with development or worsening of AF must be reported in the AF follow-up questionnaire.

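### No elimination code clearly removes a participant who receives a licensed RSV vaccine more than 30 days after dosing, so such titres would enter the Month 6 and Month 12 PPS

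*SAP*

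**What the plan says.** SAP Section 3.1.3 lists the codes that take a participant out of the PPS. Code 1040, for forbidden vaccines, has three conditions:

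- **Unregistered vaccines:** "Use of any investigational or non-registered vaccine other than the study intervention during the period beginning 30 days before the dose of study intervention". Intended later use within the trial counts as well.
- **Vaccines the protocol does not foresee:** only "in the period starting 30 days before and ending 30 days after the dose of study intervention administration", with a carve-out for influenza and COVID-19 vaccines.
- **RSV vaccines:** "Previous vaccination with an RSV vaccine, including investigational RSV vaccines".

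The code is checked at all visits. Its timing rule is "For codes 1040, 1060, 2040 and 2050: participants will be eliminated from a specific visit (at which the condition is met) onwards".

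The RSV condition has the same wording as an exclusion criterion in Protocol Section 5.2.2. The lead-in to Section 5.2 says of those criteria: "The following criteria should be checked at the time of study entry".

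The humoral persistence endpoint is the RSV-A and RSV-B GMT "at pre-study intervention administration, 1 month, 6 months and at 12 months after study intervention administration" (Protocol Table 3). SAP Section 4.3.2.2 analyses it on the PPS. An Exposed Set analysis is added if more than 5% of vaccinated participants with serology are excluded in any group.

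Protocol Section 4.2.1 justifies placebo with "As there is currently no licensed RSV vaccine available". Protocol Sections 2.3.2 and 4.2 report that the efficacy trial in adults aged 60 and over met its primary endpoint.

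**The concern.** The late visits are there to show how far titres fall after one dose. A non-study RSV vaccination between Day 31 and Month 12 bears directly on that measurement. In an RSV group it could hide waning, and a return to the post-dose level would be enough to do so. In a placebo group it would appear as a first vaccine response.

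The outputs at stake at Months 6 and 12 are:

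- GMTs, mean geometric increases and four-fold rates by group;
- the between-group GMT ratios and seroresponse differences;
- the repeated-measures model, which includes both placebo groups;
- the CMI summaries, which use the CMI subset of the PPS.

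The protocol describes a product class with efficacy already shown and no licensed vaccine at the time of writing. Availability during a 12-month follow-up is therefore a possibility the elimination rules should cover.

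**Working it through.** **Step 1. Test the case against each rule.** The case is a licensed RSV vaccine, other than the study intervention, given more than 30 days after the dose.

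| Rule | Does it apply? |
|---|---|
| Code 1040, unregistered vaccines | No. The vaccine is registered. |
| Code 1040, unforeseen vaccines | No. The window closes 30 days after the dose. |
| Code 1040, RSV vaccines | No, as an entry criterion. It has no exception for the study vaccine, so read literally at Visit 3 or 4 it would remove every RSV-group participant. It must mean vaccination before the study. |
| Code 2040 | No. It covers drugs, devices and immune-modifying treatment. |
| Code 2050 | Not clearly. It is an intercurrent medical condition code and says only that participants may be eliminated. |
| PPS definition (SAP Section 3) | No. It removes prohibited vaccination, and nothing prohibits this one. |
| Protocol Section 5.2.3 | No. It concerns exposure within another trial. |

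The complementary Exposed Set analysis would keep these titres too.

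**Step 2. Length of the uncovered period.** Take the sampling windows in code 2090 and subtract 30 days.

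- Visit 2 (30-42 days): 0 to 12 days.
- Visit 3 (180-210 days): 150 to 180 days.
- Visit 4 (350-380 days): 320 to 350 days.

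**Step 3. Possible size.** The plan has no figure on this point to reproduce. If a share f of a group is re-vaccinated before the visit, and each such titre is k times what it would have been, the mean log titre shifts by f × log k. The group GMT is then multiplied by k^f. Both f and k are assumptions.

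| k | f = 2% | f = 5% | f = 10% | f = 20% |
|---|---|---|---|---|
| 2 | 1.014 | 1.035 | 1.072 | 1.149 |
| 4 | 1.028 | 1.072 | 1.149 | 1.320 |
| 8 | 1.042 | 1.110 | 1.231 | 1.516 |

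**Step 4. Direction for a ratio.** With a common k, the OA/HA ratio is multiplied by k^(f_OA − f_HA). For k = 4, uptake of 5% in OA and none in HA gives 4^0.05 = 1.07. The reverse gives 1/1.072 = 0.93. Equal uptake gives 1.

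**Step 5. Scale.** The plan's evaluable number reproduces: 380 × 0.90 = 342 per RSV group. Ignoring the baseline covariate, the 95% CI half-width factor for a GMT ratio is 10^(1.96 × SD × √(2/342)). For an assumed log10 SD of 0.3 this is 1.11, and for 0.5 it is 1.19. The factors at 2-5% uptake are therefore no larger than ordinary sampling error. At 10-20% uptake with k of 4 or more they are comparable with it or larger.

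**Step 6. Placebo and CMI.** If every re-vaccinated placebo participant became a four-fold responder, uptake f would add at most f to that group's rate, so 5% uptake adds up to 5 points. In a CMI placebo group of about 50 (Protocol Section 6.3.4), one participant moves a percentage by 1/50 = 2 points.

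**The case against.** **The event may not occur.** The protocol says no RSV vaccine is licensed, and the documents give no uptake. All placebo participants are aged 50-59, while the cited efficacy is in adults 60 and over. OA participants are open-label and know they have had an RSV vaccine. This stands as a limit on the likely size. It does not supply the missing rule.

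**A second dose may not boost.** Protocol Section 4.3 reports that, in the earlier dose-finding study, a second dose at two months did not lift responses above the level after the first. This stands against reading the factors above as expected values in the RSV groups. The comparison there is with the post-first-dose level, whereas persistence is measured as decline from that level. Recovery to it from a waned titre is neither shown nor excluded.

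**Existing codes might stretch.** Code 1040 is checked at all visits, and Protocol Section 9.2.1 allows elimination for altered immune status. Neither names this case, and the second is discretionary. The decision would also fall after the central team is unblinded at the Day 31 analysis (Protocol Section 6.3.5).

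**Recording.** A reader of Protocol Section 6.8 alone might infer that a late RSV vaccine would go unrecorded, because after Day 30 its list turns on "All concomitant medication leading to elimination from the analysis, including products/vaccines" and on links to specified adverse events. The documents do not support that inference. The schedule of activities requires eCRF recording of vaccinations at all four visits, and Protocol Section 4.1 carries it to study end. Section 6.8 is merely narrower than those two.

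**Conclusion.** The gap holds. Applied as written, the elimination codes keep a participant with a late licensed RSV vaccination in the Month 6 and Month 12 PPS.

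Its size is unknown. At 2-5% uptake with a 4- to 8-fold rise over the waned titre the group GMT factor is 1.03-1.11, and at 10% uptake it is 1.15-1.23. These figures rest entirely on assumed uptake and boost.

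Two stronger readings go too far:

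- A reader might infer that the OA/HA and OA/AIR ratios would be inflated. The direction depends on which group has more uptake, so the ratios could be distorted either way.
- A reader might infer that the non-inferiority conclusions are at risk. Those tests use Day 31 titres, where the uncovered period is at most 12 days. The late comparisons are secondary, descriptive and unadjusted for multiplicity.

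This is an inexpensive improvement to the analysis rules and does not call the design into question.

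**What to change.** **SAP Table 2, code 1040.** Add a condition: receipt of any RSV vaccine other than the study intervention at any time from Day 1 to Visit 4, with elimination from the next sampling visit onwards. The code's existing timing and all-visit check accommodate this. It is an analysis rule only and does not restrict what a participant may receive.

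**Protocol Section 6.8.** Align its list with the schedule of activities and Section 4.1, so that vaccination recording to study end is stated the same way in all three places. No new data collection is needed.

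**Cost.** A few participants leave the late PPS. At an assumed 5% uptake, 342 × 0.95 ≈ 325 remain per RSV group, and 171 × 0.95 ≈ 162 per placebo group (171 = 190 × 0.90, applying the same attrition). At 10% the figures are about 308 and 154. At zero uptake nothing is lost. The removals count towards the 5% threshold for the Exposed Set analysis, which would still show results with these titres included.
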